1.4.1 Hypotheses

- Consolidation with 4 cycles of IRD will be well tolerated and will result in \geq 15% improvement in MRD-negative rate
- MRD-negativity after 4 cycles of IRD consolidation will be associated with an improved PFS and OS
- Maintenance therapy with ixazomib will be well tolerated and will be similar in response rate, PFS, OS, and MRD-positive to MRD-negative conversion rate to maintenance therapy with lenalidomide.

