15.1 Determination of Sample Size

A power analysis was performed for the primary objective. The smallest increase in MRD-negative rate after four cycles of IRD that would warrant further investigation is 10%, with a result of $\leq 9\%$ being considered ineffective. Based on a meta-analysis of five prior studies in this population, the expected MRD-negative rate at Day 100 post-transplant is ~50%. If the true rate of MRD-negative is 40-60% at the Day 100 post-transplant visit, 220 evaluable patients will detect a 10% improvement in MRD-negative rate with 90% power at 1-sided 0.05 alpha. Due to highly varied data of baseline MRD (i.e., 5 published studies showed MRD-negative rates ranged from 8% to 62%) as well as the lack of pilot information for the association over time, we currently choose a rather conservative estimation and the sample size is estimated using non-paired design instead. However, an interim analysis will be performed when ~50 patients are randomized to maintenance arms, and sample size adjustment will then be made if needed (see details below for interim analysis).

The randomized maintenance portion of the study will provide pilot data that will be used to design future studies. Although the study was not powered to show non-inferiority or superiority of either of the two maintenance arms, the designed sample size (n=110 evaluable patients/arm) will provide us a reasonable power for our hypothesis that "Maintenance therapy with ixazomib will be well tolerated and will be similar in response rate, PFS, OS, and MRD-positive to MRD-negative conversion rate to maintenance therapy with lenalidomide". Taking PFS as an example, the recent meta-analysis of lenalidomide versus placebo/observation showed that the 5-year cumulative incidence of events (PD or 2nd-line treatment) was ~54%. [29] The figure below illustrates the statistical power to show non-inferiority given the "true" difference of event rates (e.g., death or recurrence or treatment failure) between the ixazomib arm (experimental group) and lenalidomide arm (control group). With a non-inferiority margin of 10% in 5-year PFS (or equivalently a hazard ratio (HR) of 1.3), for example, the designed sample size would allow 80% power to claim non-inferiority when a slightly better PFS is observed in the ixazomib arm.

This power analysis was based on a simulation study where

- the true rate in the experimental treatment (ixazomib) varied from 45% to 65%;

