- the true recurrence rate in the control (lenalidomide) varied from 52% to 56%;
- a total of 10,000 replicates are generated under each scenario, and each replicate includes N=110 ixazomib patients and N=110 lenalidomide patients;
- events in each arm were generated following binomial distributions;
- 1-sided 90% confidence interval (CI) for the difference between event rates was calculated and non-inferiority will be declared if the upper boundary of CI is below 10% [30]. That is, the non-inferiority margin was set as 10% absolute difference, or equivalently a hazard ratio (HR) of 1.3 when assuming the time following an exponential distribution;
- The figure shows average power as a function of the true difference of event rates between experimental and control groups;
- Note that the current simulation was based on binary data for simplicity. We expect that more power could be achieved in the actual time-to-event analysis due to the availability of richer information (i.e., not only the status of event, but also the exact time when it happens).

The accrual rate over six participating centers will be roughly 6 patients per month, with a total accrual timeframe of about 3 years following study activation.

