15.2 Randomization and Stratification

Following initial treatment with IRD consolidation therapy, patients will be randomized to a pilot portion of the study evaluating ixazomib or lenalidomide as maintenance therapy.

Patients will be restaged following completion of consolidation treatment and will be randomized on a 1:1 basis to maintenance therapy with ixazomib or lenalidomide. Patients will be stratified based on MRD status at restaging (MRD-negative v. MRD-positive). For the purposes of randomization, if there are discrepant results from the Mayo Clinic MFC and the Adaptive ClonoSEQ MRD tests, the Adaptive ClonoSEQ results will be used for stratification. In the event that the Adaptive ClonoSEQ results are not available, the Mayo Clinic MFC results will be used for stratification, and vice versa.

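### Section 15.1's non-inferiority power claim for maintenance is too favourable: about 58% if the arms are equal, and 80% only with a true ixazomib advantage of about 4.3 points

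*Combined protocol and SAP*

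**What the plan says.** The third hypothesis in Section 1.4.1 is that ixazomib maintenance "will be similar in response rate, PFS, OS, and MRD-positive to MRD-negative conversion rate to maintenance therapy with lenalidomide". Section 15.1 repeats it. After conceding that the study was not powered for non-inferiority or superiority between the maintenance arms, the section says that 110 evaluable patients per arm "will provide us a reasonable power for our hypothesis that" the arms are similar. With PFS as the example, it then states that "the designed sample size would allow 80% power to claim non-inferiority when a slightly better PFS is observed in the ixazomib arm".

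The basis is a simulation described in the same section. Events are binomial and "each replicate includes N=110 ixazomib patients and N=110 lenalidomide patients". The true lenalidomide rate runs from 52% to 56% and the true ixazomib rate from 45% to 65%. A "1-sided 90% confidence interval (CI) for the difference between event rates was calculated". The decision rule applied to this limit is that "non-inferiority will be declared if the upper boundary of CI is below 10" percentage points, which the section equates to a hazard ratio of 1.3. The section closes with: "We expect that more power could be achieved in the actual time-to-event analysis due to the availability of richer information".

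**The concern.** If the hypothesis is similarity, the relevant power is the power when the true rates are the same or nearly so. The text does not give it. It gives 80% under a condition described only as slightly better, and attaches that condition to the observed rather than the true result. Someone planning a later trial could take 110 per arm as adequate for showing that similar treatments are similar. Section 15.1 itself says that these data will be used to design future studies.

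**Working it through.** **Inputs (Section 15.1).** n = 110 per arm. Lenalidomide 5-year event rate about 54%, varied over 52-56%. Margin 10 points. One-sided 90% limit, so z = 1.2816. The interval method is the one in the reference cited there (Newcombe).

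**Step 1: reproduce the stated 80%.** Let d be the true ixazomib rate minus the true lenalidomide rate. Under a normal approximation,

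power = Φ((0.10 − d)/SE − 1.2816), with SE = √[(pL(1 − pL) + pI(1 − pI))/110].

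The text gives no d for its 80%, so I solved for it. At d = −0.043 (54.0% against 49.7%), SE = √[(0.2484 + 0.2500)/110] = 0.0673. Power is Φ(0.143/0.0673 − 1.2816) = Φ(0.84) = 80%. Reversing the formula, n = (1.2816 + 0.8416)² × 0.4984/0.143² ≈ 110 per arm. The 80% is reproduced, at an advantage of 4.3 points. Under exponential times this is a hazard ratio of ln(0.503)/ln(0.46) = 0.885.

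**Step 2: power when the arms are equal.** SE = √(2 × 0.54 × 0.46/110) = 0.0672. Power is Φ(0.10/0.0672 − 1.2816) = Φ(0.206) = 58.2%.

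**Step 3: exact check.** Enumerating both binomials with the Newcombe limit, averaged over lenalidomide rates of 52-56%:

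| True difference, ixazomib minus lenalidomide | Power |
|---|---|
| 0 | 58.0% |
| −1 point | 63.7% |
| −2 points | 69.2% |
| −3 points | 74.2% |
| −4 points | 78.7% |
| −4.3 points | 80.0% |

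At a true difference of +10 points the rule passes 9.7% of the time, close to the nominal 10%, which supports the reconstruction. A simulation gave 57.7% for equal arms. This is also the favourable reading of the interval: taken as a two-sided 90% interval (one-sided 5%), power for equal arms is 42-44% and 80% needs 6.7-7.0 points.

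**Step 4: sample size for 80% with equal arms.** n = (1.2816 + 0.8416)² × 2 × 0.54 × 0.46/0.10² = 224 per arm, about twice the design.

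**Step 5: 'observed' against 'true'.** The rule is met when the observed difference is below about 0.10 − 1.2816 × 0.0672 = 0.0139, or +1.4 points. One extra ixazomib event is 1/110 = 0.9 points and passes; two extra are 1.8 points and do not. Any observed ixazomib advantage therefore passes, so an 80% chance conditional on an observed advantage has no meaning.

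**Step 6: the time-to-event sentence.** A 10-point margin at 54% is a hazard ratio of ln(0.36)/ln(0.46) = 1.316, which the text rounds to 1.3. With equal arms, power = Φ(ln(margin) × √events/2 − 1.2816). At 5 years, events ≈ 0.54 × 220 = 119.

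| Events | Margin 1.3 | Margin 1.316 |
|---|---|---|
| 119 | 55.9% | 58.5% |
| 155 | 64% | 67% |
| 161 | 65% | 68% |

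The counts of 155 and 161 are assumptions. On an exponential curve through 54% at 5 years (hazard 0.7765/5 = 0.1553 per year) they correspond to about 7.9 and 8.5 years of follow-up: −ln(1 − 155/220)/0.1553 and −ln(1 − 161/220)/0.1553. For 80% with equal arms, the events needed are 4 × 2.1232²/(ln margin)² = 262 at 1.3, or 240 at 1.316. Both exceed the 220 patients.

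**The case against.** The best defence is that nothing here is miscalculated. The 80% reproduces, and whether 4.3 points is slight or 58% reasonable is a matter of judgement. The sentence that claims reasonable power opens by saying that the comparison was not powered, and the maintenance part is called pilot throughout. The power curve is in a figure not available to this review. It is described as showing power against the true difference, and the simulated rates include both equality and −4.3 points, so it may well display these values. The neighbouring text uses 'true' correctly, so 'observed' may be a slip.

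Much of this stands. It limits the weight of the point but does not repair the prose: a disclaimer followed by a claim of reasonable power leaves the reader with the claim, and a figure showing 58% would sit badly beside it.

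Three stronger readings are tempting and should not be drawn.

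- A reader might infer that the trial will fail its own non-inferiority test about four times in ten if the arms are equal. Section 15.3 plans no such final test, only log-rank, chi-square and Fisher comparisons. The rule belongs to the power calculation. The futility rule in Section 15.4 uses the observed hazard ratio, not a confidence limit.
- A reader might infer from 56% against 58% that time-to-event analysis loses power. That compares margins of 1.3 and 1.316. At the matched margin the 5-year figures agree (58.5% against 58.2%), and longer follow-up does add power, so the section's expectation is not wrong.
- A reader might want low power figures for OS and MRD conversion. The documents give no death rate, conversion rate or conversion margin from which to compute them. What can be said is that no calculation is described for these endpoints or for response.

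**Conclusion.** The point holds as an overstated and imprecise power statement, not as an arithmetic error. Under Section 15.1's own assumptions, 110 per arm gives about 58% power to show non-inferiority in 5-year PFS when the arms are equal. It gives 80% only with a true advantage of about 4.3 points, over two-fifths of the margin. Time-to-event analysis leaves power at about 56-59% at 5 years. It raises it to about 64-68% if 155-161 events accrue, still short of 80%.

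These figures rest on 110 patients per arm, a lenalidomide rate of 52-56%, a one-sided 90% limit and, for the hazard-ratio figures, exponential times. The consequence is minor: the comparison is secondary and pilot, and the primary objective is untouched.

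**What to change.** In Section 15.1:

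1. Replace the power sentence with: 'With 110 per arm and a one-sided 90% limit, power to show non-inferiority in 5-year PFS is about 58% if the arms are equal, and 80% if the true 5-year event rate on ixazomib is about 4.3 points lower (HR about 0.88).' This also replaces 'observed' with 'true'.
2. Limit the power statement to PFS, since no calculation is described for response, OS or MRD conversion.
3. Keep the time-to-event sentence but qualify it: about the same power at 5 years (about 119 events), with a gain only from longer follow-up (about 64-68% if about 155-161 events accrue, an assumed count), and below 80% for equal arms in either case.

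The cost is protocol wording only. The stated power becomes less favourable. No patients, procedures or analyses change.

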15.2 Randomization and Stratification

Following initial treatment with IRD consolidation therapy, patients will be randomized to a pilot portion of the study evaluating ixazomib or lenalidomide as maintenance therapy.

Patients will be restaged following completion of consolidation treatment and will be randomized on a 1:1 basis to maintenance therapy with ixazomib or lenalidomide. Patients will be stratified based on MRD status at restaging (MRD-negative v. MRD-positive). For the purposes of randomization, if there are discrepant results from the Mayo Clinic MFC and the Adaptive ClonoSEQ MRD tests, the Adaptive ClonoSEQ results will be used for stratification. In the event that the Adaptive ClonoSEQ results are not available, the Mayo Clinic MFC results will be used for stratification, and vice versa.

15.3 Data Analysis

For the analysis of consolidation therapy, the data for safety analysis will include these patients who have at least 1 dose of IRD consolidation therapy, while the data for efficacy analysis will include patients who complete 4 cycles therapy. Demographic and clinical characteristics of the sample, as well as adverse events, complications and loss to follow-up will be summarized using descriptive statistics. The change of MRD-negative rates for pre- and post-consolidation therapy will be described using contingency table and compared by McNemar test. The incidences of mortality, progression, relapse, as well as tumor response (complete response and overall) and their 95% confidence intervals following consolidation therapy will also be calculated.

Data analysis for maintenance portion will be performed following the intent-to-treat (ITT) principle. The balance of demographic and baseline clinical characteristics between two arms will be compared using t-test, Mann-Whitney rank-sum test, or Chi-square test as appropriate. The distributions of responses and adverse events across two arms will be summarized using contingency tables and compared by 2-sample Chi-square test or Fisher's exact test. Contingency table and Fisher's exact test will also be used to assess the between-arms difference for the rates of conversion from MRD-positive to MRD-negative. Chi-square test will be used to compare the distribution of responses, and Kaplan-Meier curves with log rank tests will be used to compare PFS and OS.

Overall survival (OS) will be defined as time from ASCT to death due to any causes, and survivors will be censored at withdrawal or study closeout. Progression-free survival (PFS) will be defined as time from ASCT to progression, relapse, or death, whichever occurs first, and those event-free survivors will be censored at withdrawal or study closeout. The between-arm differences in OS and PFS will be described using Kaplan-Meier product limit estimator and compared by log-rank tests. Kaplan-Meier curves will also be used to describe the association between MRD status (both prior to and after consolidation therapy) and OS or PFS, and proportional hazards Cox models will be used to control the potential confounding effects of other patient and clinical characteristics.

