1.4 Study Rationale

Based on the further need to improve PFS and OS post-ASCT for multiple myeloma and the benefits seen of consolidation/maintenance treatment with immunomodulatory drugs thalidomide and lenalidomide and the proteasome inhibitor bortezomib, the natural next step is to evaluate combination regimens of immunomodulatory drugs and proteasome inhibitors as consolidation/maintenance post-ASCT. The regimen consisting of ixazomib, lenalidomide, and dexamethasone (IRD) has been shown to have low toxicity, and the availability of an oral formulation of ixazomib allows for easier administration when compared to bortezomib.

In this study, following consolidation with IRD, patients will be randomized to maintenance therapy with lenalidomide or ixazomib in order to collect pilot data comparing the toxicity and efficacy of maintenance therapy with immunomodulatory drugs and proteasome inhibitors.

The proposed study would:

- 1) Provide data on the efficacy and tolerability of IRD as consolidation post ASCT;
- 2) Provide data on the value of MRD-negativity as a surrogate for PFS and OS;
- 3) Provide data on the efficacy and tolerability of single agent ixazomib as maintenance therapy post-ASCT;
- 4) Provide pilot data that could generate hypotheses for a larger phase III study designed to conclusively address the value of IRD consolidation and single agent ixazomib maintenance.

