2.0 OBJECTIVES

2.1 Primary Objective

To determine the improvement in MRD-negative rate after 4 cycles of IRD consolidation.

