2.2 Secondary Objectives

1. To determine the MRD-negative rate after ASCT
2. To evaluate the toxicity, response rate, PFS, and OS of IRD consolidation
3. To collect pilot data to compare toxicity, response rate, PFS, OS, and the rate of MRD-positive to MRD-negative conversion between the two maintenance arms
4. To evaluate the association of PFS and OS with MRD-negativity and MRD-positivity prior to consolidation and after 4 cycles of IRD consolidation

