9.0 CENTRAL LABS

9.1 Mayo Clinic MFC MRD Panel

Approximately 5 ml of bone marrow aspirate in EDTA (pink top) tube(s) will be collected at the following time points:

- Prior to beginning consolidation therapy
- Prior to beginning maintenance therapy
- Cycle 13 Day 1 of maintenance therapy
- Cycle 25 Day 1 of maintenance therapy*
- Cycle 37 Day 1 of maintenance therapy*

*- Only required for patients in suspected or confirmed CR/sCR at that time

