15.4 Interim Analysis

Two interim analyses will be performed during the consolidation phase of the trial. The first will occur when ~50 patients complete the consolidation therapy and are randomized to maintenance portion. The second will occur in Year-3, after approximately 150 evaluable patients complete the consolidation therapy and are randomized to maintenance portion.

The data analysis will be descriptive in nature. The change of MRD-negative rates for pre- and post-consolidation therapy will be estimated using contingency table. Sample size will be re-estimated and conditional power will also be calculated based on the accumulated data. Conditional power is defined as the projected power to reject the null hypothesis at the end of study given the data accrued up to a specific interim analysis.

Therefore, a high value of conditional power indicates a highly likely, if not inevitable, conclusion to reject the null hypothesis given the available information. Similarly, a small value suggests a high possibility of negative finding given the current data. This interim analysis will assist investigators on the decision whether the sample size (220 evaluable, ~240 total) needs to be adjusted.

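### Consolidation efficacy, including the primary MRD comparison, is planned only in patients who complete four cycles of IRD, with no supportive all-treated analysis of MRD or response

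*Combined protocol and SAP*

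**What the plan says.** Section 15.3 sets two populations for consolidation. Safety covers everyone who took at least one dose of IRD; for efficacy, "the data for efficacy analysis will include patients who complete 4 cycles therapy". The same paragraph then gives the McNemar comparison of MRD-negative rates before and after consolidation, which is the analysis of the primary objective. It also plans "The incidences of mortality, progression, relapse, as well as tumor response" after consolidation. Intent-to-treat is stated only for the maintenance portion.

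The objectives are worded differently from one another:

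- Section 2.1 (primary): "To determine the improvement in MRD-negative rate after 4 cycles of IRD consolidation".
- Section 2.2 (secondary objective 2): "To evaluate the toxicity, response rate, PFS, and OS of IRD consolidation".
- Section 1.4 (aim): "Provide data on the efficacy and tolerability of IRD as consolidation post ASCT".

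Only the first carries a four-cycle condition.

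Section 5.7 lists progression, death and adverse events among the reasons for removal. Sections 9.1 and 9.2 schedule the second MRD marrow "Prior to beginning maintenance therapy". Note 4 of the Section 8.0 calendar ties that restaging visit to completion of cycle 4, and the calendar marks no MRD marrow at End of Study. Under Section 5.1, patients who stop ixazomib or lenalidomide for toxicity during consolidation are not randomized but can go on to the other maintenance arm.

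**The concern.** Whether a patient completes four cycles depends partly on how the patient fares. Someone who stops all IRD for progression, death or toxicity leaves both the numerator and the denominator of the MRD comparison. The result then describes patients able to finish, while secondary objective 2 and Section 1.4 ask about IRD as given. Intent-to-treat in maintenance cannot restore these patients, because that portion starts after consolidation.

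Two definitions are also missing. Section 15.0 counts patients *evaluable* for the primary objective and Section 15.3 counts patients who complete four cycles, but the plan does not link the two. A patient who drops one drug and goes on to maintenance has a planned second MRD sample, yet nothing says whether that patient is evaluable or a completer. No rule covers a patient with no second MRD result. Left open, these choices would be made after the data are seen.

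**Working it through.** **Inputs from the documents.** 220 evaluable patients of about 240, with more than 90% of treated patients expected to be evaluable (Section 15.0). Expected MRD-negative rate about 50% near Day 100; a 10-point gain, 90% power, one-sided alpha 0.05 (Section 15.1). Hypothesised gain of at least 15% (Section 1.4.1).

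**Assumptions.** The documents give neither the share of non-completers nor their MRD results. *Evaluable* may also allow for missing samples or failed assays, so 20 non-completers is an assumption.

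**1. The plan's own figures.** 220/240 = 91.7%, consistent with more than 90%, and leaves 20 patients (8.3%). The 90% power reproduces as an exact one-sample binomial test with n = 220 against a fixed baseline: 90.0% (40% to 50%), 90.4% (50% to 60%) and 91.8% (60% to 70%).

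**2. Gain in all treated patients.** Let g be the completer gain, f = k/240 the non-completer share, and b the non-completers' baseline MRD-negative rate.

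- Same gain as completers: g
- Status unchanged: g × (1 − f)
- All counted as not MRD-negative: g × (1 − f) − f × b

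For k = 20 and g = 10 points: 10 × 220/240 = 9.17. With b = 50%: 9.17 − (20/240) × 50 = 9.17 − 4.17 = 5.0.

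For k = 20 and g = 15 points: 15 × 220/240 = 13.75. With b = 50%: 13.75 − 4.17 = 9.58.

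| g (points) | k of 240 | Status unchanged | Not negative, b = 25% | Not negative, b = 50% |
|---|---|---|---|---|
| 10 | 10 | 9.6 | 8.5 | 7.5 |
| 10 | 20 | 9.2 | 7.1 | 5.0 |
| 10 | 24 | 9.0 | 6.5 | 4.0 |
| 15 | 10 | 14.4 | 13.3 | 12.3 |
| 15 | 20 | 13.75 | 11.7 | 9.6 |
| 15 | 24 | 13.5 | 11.0 | 8.5 |

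With b = 0 the strict rule gives the same result as unchanged status. The row k = 24 is exactly 10% and so lies just outside the plan's expectation. These are illustrations, not bounds.

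**3. Effect on the test.** For a 10-point completer gain, McNemar power is Φ[(d√n − 1.645√p) / √(p − d²)], where d is the net gain and p the discordant proportion. The documents give no discordance; 20%, 25% and 30% in completers are assumed.

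| Set and rule (k = 20) | 20% | 25% | 30% |
|---|---|---|---|
| Completers, n = 220 | 95.7% | 91.1% | 86.0% |
| All treated, n = 240, baseline carried forward | 95.6% | 91.1% | 86.0% |
| All treated, not negative, b = 25% | 78.6% | 71.1% | 64.6% |
| All treated, not negative, b = 50% | 49.5% | 43.7% | 39.4% |

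Carrying baseline forward adds no discordant pairs, so it lowers the estimate and leaves the test essentially unchanged. The strict rule turns baseline-negative patients into losses, which lowers both.

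**The case against.** The strongest reply is that the efficacy set matches the primary question. The objective, the hypothesis and the sizing are all framed on the rate after four cycles, and the documents never claim that gain for every patient given IRD. This stands: a reader might infer that the primary analysis uses the wrong population, but it answers the primary objective as worded.

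A reader might also infer that early deaths and progressions drop out of PFS and OS. The documents do not establish this. Section 15.3 defines both from ASCT in a separate paragraph with no completer limit. Section 5.8 and calendar notes 8 and 15 follow removed patients for 18 months, with PFS and OS assessed. Deaths also fall under safety, which covers all treated patients. What remains is that the set for these outcomes is not stated, and the mortality and progression incidences sit in the paragraph that sets the completer rule.

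A third inference is that the choice of population carries the result across a decision line. Section 15.1 says "The smallest increase in MRD-negative rate after four cycles of IRD that would warrant further investigation is 10" per cent and calls 9% or less ineffective, but this is sizing language, not a rule applied to the point estimate. At n = 220, a 10-point gain and 20–30% discordance, the 95% interval is about ±5.8 to ±7.1 points (1.96 × √[(p − 0.01)/220]). The 0.8-point shift for 20 patients with unchanged status is well inside it.

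Finally, counting a patient who merely lacks a second sample as not MRD-negative can record a loss that nobody observed. That is a fair criticism for toxicity stops and failed assays. The 5.0-point figure depends on that rule, so it should not be the main one.

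**Conclusion.** The point holds as a gap in the plan for consolidation efficacy, not as a fault in the primary test. Completer-only analysis leaves secondary objective 2 and the Section 1.4 aim without an all-treated MRD or response result. Overstatement of the gain among all treated patients requires that non-completers gain less; if they gain equally there is none. With 20 of 240 non-completers, it is 0.8 points on a 10-point gain or 1.25 on a 15-point gain if their status is unchanged. It is 5.0 or 5.4 points if all count as not MRD-negative from a 50% baseline. The number of non-completers, their baseline rate and their outcomes are all assumed.

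Two further inferences should be resisted. The between-arm maintenance comparison is not biased by this rule, since it follows intent-to-treat after randomization. Nor does Section 15.4 create another analysis set: "The first will occur when ~50 patients complete the consolidation therapy and are randomized to maintenance portion" fixes when an interim look takes place.

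**What to change.** Keep the McNemar analysis in four-cycle completers as primary, and make these changes in Section 15.3 before the data are analysed:

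- **Supportive set.** Prespecify an MRD analysis in patients with at least one dose of IRD and a pre-consolidation MRD result.
- **Observed results.** Use any actual post-consolidation result, including from patients who dropped one drug and went on to maintenance.
- **No result because of progression or death.** Count as not MRD-negative.
- **No result for other reasons (toxicity stops, failed assays).** Show baseline carried forward and not MRD-negative side by side as a sensitivity range, with neither as the main rule.
- **Other outcomes.** State that response, mortality, progression, PFS and OS of consolidation are reported in all treated patients.
- **Definitions.** Define *evaluable* and completion of four cycles, and say whether patients who drop one drug count as each.

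The cost is definitions and extra tables, with no new procedures; results that were never obtained stay missing and are handled by the rules above. The reported all-treated gain may be somewhat smaller. Power in the supportive analysis can fall under the strict rule: with 20 non-completers and a 10-point completer gain, from 86–96% to 65–79% at a 25% baseline rate or 39–50% at a 50% baseline rate. The plan should say so, and the primary analysis is unaffected.
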